- m. Renal function blood tests include creatinine, blood urea nitrogen, and serum cystatin C.
- n. Quantitative urine analysis includes KIM-1 and urinalysis (pH, specific gravity, protein, glucose, ketones, cytology, and hemoglobin).
- o. A 2-week window is allowed in the event the child is unable to complete this assessment at a given visit.

Note: Rollover Instructions:

- Subject is able to rollover within 1 week (7 calendar days) from main to OLE
 - Main study Week 96 study assessments will be used as Baseline assessments in OLE
 - No safety follow-up visit needed for main study
- Subject rolls over to OLE more than 7 days after conclusion of main study
 - All baseline assessments to be performed fresh for OLE study
 - No safety follow-up visit needed for main study if rollover/ICF for OLE occurs within 4 weeks of main study Week 96
 - If rollover/ICF occurs more than 4 weeks after Week 96 of main study, perform safety follow-up visit

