10.3.4.2. Safety Monitoring for Renal Function

Renal tests need to be monitored as specified in the Schedule of Events ([Table 2](#)). Patients with the following test results need to undergo repeat testing for confirmation of abnormal test results:

- Protein $\geq 2+$ (dipstick)
- Urine Protein to Creatinine Ratio $\geq 150\text{mg/g}$
- Urine Albumin to Creatinine Ratio $\geq 30\text{mg/g}$
- Serum Creatinine $\geq 0.3 \text{ mg/dL}$ above baseline
- Serum Creatinine $\geq 1.5 \times$ ULN
- Estimated glomerular filtration rate (eGFR) $\leq 60 \text{ ml/min}/1.73\text{m}^2$
- Red blood cells (RBCs) $> 1/\text{hpf}$
- Elevated Cystatin C $>$ ULN
- Elevated kidney injury molecule 1 $>$ ULN

Additional Investigations:

24-hour urine collection needs to be undertaken to quantify any proteinuria and glomerular filtration rate (GFR) changes indicated by confirmed results as above. Additional evaluations including nephrology consultation, renal US/CT/MRI, renal biopsy, may be performed at the discretion of the Investigator in consultation with the Sponsor Medical Monitor.

Stopping Rules for Renal Test Results:

In the event of laboratory results meeting the following criteria, **and the event is without an alternative explanation as discussed with the Sponsor Medical Monitor**, dosing of a patient with eteplirsen will be stopped permanently:

- Quantitative total urine protein measurement of $\geq 1 \text{ g}/24 \text{ hours}$
- Measured GFR (creatinine clearance) $\leq 45 \text{ mL/min}/1.73\text{m}^2$
- Gross hematuria
- Any RBC Casts
- Persistent microscopic hematuria $\geq 3 \text{ RBCs/hpf}$ for 3 consecutive weeks

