10.3.5. Clinical Safety Laboratory Evaluations

The following routine clinical safety laboratory tests will be collected at the time points specified in [Table 2](#), samples prepared according to the Laboratory Manual provided for the study, and results analyzed by an accredited central laboratory selected by the Sponsor:

Chemistry: Sodium, chloride, potassium, calcium, glucose, creatinine, blood urea nitrogen, albumin, uric acid, total bilirubin, alkaline phosphatase, amylase, alanine aminotransferase, aspartate aminotransferase, GGT, GLDH, C-reactive protein, creatine kinase (CK), and serum cystatin C

Hematology: Complete blood count with differential

Coagulation Screen: Prothrombin time, International Normalized Ratio, and activated partial thromboplastin time

Persistent, unexplained abnormalities on routine renal blood test monitoring will result in additional renal function tests such as eGFR and 24-hour urine testing for protein.

A description of blood volumes to be drawn is provided in Section 17.1.

Any value outside of the current reference ranges for the laboratory performing the test will be flagged on the laboratory results. The Investigator will determine whether abnormal assessment

results are clinically significant or not. Clinical significance is defined as any variation in assessment results that has medical relevance resulting in an alteration in medical care. If clinically significant deterioration from Baseline levels is noted, the Investigator will continue to monitor the patient with additional assessments until:

- Values have reached normal range and/or Baseline levels, or
- In the judgment of the Investigator together with the Sponsor Medical Monitor, abnormal values are assessed to be not related to the administration of IP or other protocol-specific procedures, and additional assessments are not medically indicated.

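### Two of the three urine-protein triggers in Section 10.3.4.2 need urine creatinine or urine albumin, which the scheduled urine panel does not list

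*Combined protocol and SAP*

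**What the plan says.** Section 10.3.4.2 opens with "Renal tests need to be monitored as specified in the Schedule of Events", that is, Table 2. It then lists results that call for repeat testing. Three of them measure protein in urine: dipstick protein of 2+ or more, "Urine Protein to Creatinine Ratio" of at least 150 mg/g, and "Urine Albumin to Creatinine Ratio" of at least 30 mg/g. For confirmed results it says "24-hour urine collection needs to be undertaken to quantify any proteinuria and glomerular filtration rate (GFR) changes indicated by confirmed results as above".

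Two later rules are expressed per 24 hours. One permanent stopping criterion in Section 10.3.4.2 is "Quantitative total urine protein measurement of" 1 g/24 hours or more. Section 11.3.9 makes proteinuria above 500 mg/24 hr a nephrotoxicity adverse event of special interest (AESI), to be reported to the sponsor within 24 hours of awareness.

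Table 2 schedules a urine dipstick and, in a separate row, a quantitative urine analysis. Footnote n gives the content of the latter: "Quantitative urine analysis includes KIM-1 and urinalysis (pH, specific gravity, protein, glucose, ketones, cytology, and hemoglobin". Footnote m lists creatinine, blood urea nitrogen and cystatin C as blood tests. Section 10.3.5 lists chemistry, hematology and coagulation panels but no urine panel. It adds that the listed tests have "samples prepared according to the Laboratory Manual provided for the study".

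**The concern.** A trigger can fire only if its inputs are measured. Both ratios have urine creatinine as denominator, and one has urine albumin as numerator. If a site runs exactly what Table 2 lists, neither ratio exists and neither trigger can operate, although Section 10.3.4.2 sends the reader to Table 2 for the tests.

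The quantitative urine protein that is scheduled does not fill the gap, because Section 10.3.4.2 gives it no spot-sample threshold of its own.

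What is at stake is classification. Section 5.5 names proteinuria as a risk of the drug. Section 7.3.1 makes the incidence of AESIs, including renal events, a safety endpoint under the primary objective in Section 6.1. A boy who never has a 24-hour collection cannot be classed as a proteinuria AESI or checked against the 1 g/24 hours rule. Any such loss can only lower the renal AESI count. With at most 15 boys, one unclassified case is worth up to 1/15 = 6.7 percentage points of incidence, if all 15 enroll and are dosed.

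**Working it through.** The plan gives no figure to reproduce. The check breaks each urine-protein trigger into the analytes it needs and compares them with every test listed in Table 2 (footnotes b, m and n) and Section 10.3.5.

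| Trigger (10.3.4.2) | Needs | Listed as a urine test? | Evaluable from listed tests? |
|---|---|---|---|
| Dipstick protein 2+ or more | Dipstick | Yes, own row in Table 2 | Yes |
| Protein/creatinine at least 150 mg/g | Urine protein; urine creatinine | Protein yes; creatinine no | No |
| Albumin/creatinine at least 30 mg/g | Urine albumin; urine creatinine | Neither | No |

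The creatinine in footnote m and the creatinine and albumin in the Section 10.3.5 chemistry panel are blood tests, so they cannot supply a urine ratio. Result: 1 of 3 triggers can be evaluated and 2 of 3 cannot.

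**Other routes to a 24-hour collection.** Section 10.3.4.2 also has triggers on serum creatinine (two criteria), eGFR, red cells per high-power field, cystatin C and KIM-1. Section 10.3.5 adds 24-hour urine protein after persistent, unexplained renal blood abnormalities. None of these starts from urine protein. The exposed case is therefore a boy whose only abnormality is proteinuria below 2+.

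**Samples affected.** The quantitative urine row of Table 2 is marked at Baseline, Week 1, every 12 weeks from Week 12 to Week 276, and Week 284.
- Twelve-weekly visits: (276 − 12)/12 + 1 = 23
- Visits per boy: 1 + 1 + 23 + 1 = 26
- Samples for 15 boys: 26 × 15 = 390
- Assays for two analytes: 390 × 2 = 780

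**Where proteinuria below 2+ could lie (illustration only).** Assume that 2+ starts at about 100 mg/dL and that urine volume is 0.5 to 1.0 L/day (5 to 10 dL). Neither figure is in the documents.
- 1 g/24 hours: 1000/10 = 100 mg/dL to 1000/5 = 200 mg/dL, at or above 2+
- 500 mg/24 hr: 500/10 = 50 mg/dL to 500/5 = 100 mg/dL, mostly below 2+

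On these assumptions the dipstick largely covers the stopping rule, though a dilute spot sample could still miss it. The exposure lies mainly in a band around the AESI level.

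**The case against.** The strongest reply is that footnote n is shorthand. Its verb is *includes*, and Section 10.3.4.2 itself names both ratios among the test results to act on, so the authors evidently expected them to be available. The Laboratory Manual, which is not among the documents, may specify them. This stands as a limit: the documents show a mismatch between the trigger list and the listed panel, but not that the ratios go unmeasured. It does not remove the point, because Section 10.3.4.2 refers to Table 2 and nothing in the protocol gives a visit, sample or assay for either ratio.

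A second reply is that a boy with abnormal urine protein is not ignored. Section 10.3.5 has out-of-range laboratory values flagged, the investigator must judge clinical significance, and clinically significant deterioration leads to additional assessments. Clinically significant urinalysis is an endpoint in Section 7.3.1, an abnormality that alters care is an adverse event under Section 11.2.1, and the DMC reviews safety data on an ongoing basis (Section 9.6). All of this stands. A reader might infer that proteinuria is unmonitored, and the documents do not support that. None of these steps mandates a 24-hour collection, however, and the DMC's laboratory assessments of interest in Section 10.3.5.1 have no urine-protein criterion.

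A third reply concerns counting. It is tempting to say that 2 of all 9 renal triggers cannot be evaluated. That count is uneven: footnote n does not list microscopy for red cells either, so a literal reading applied to the ratios should apply there too. The count of 2 of the 3 urine-protein triggers avoids this.

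A last reply is burden. Assuming urine creatinine of 0.1 to 0.5 g/day (not in the documents), 150 mg/g corresponds to 150 × 0.1 = 15 mg to 150 × 0.5 = 75 mg of protein per day, which is 3% to 15% of the 500 mg AESI level. Some boys would face collections well below that level. This is a real cost, but it follows from the protocol's own threshold and not from listing the assay.

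**Conclusion.** The point holds as a mismatch within the protocol. Run exactly as listed, two stated safety triggers could never fire, and dipstick protein of 2+ or more would be the only urine-protein trigger for the 24-hour collection. The gap would apply to every scheduled quantitative urine sample, up to 390 in all.

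Its practical effect is unproven and probably narrow. It requires that the Laboratory Manual does not already cover the ratios, that the boy meets no other renal trigger, and that the investigator does not order the collection on judgement. A reader might conclude that the 1 g/24 hours stopping rule is disabled. The documents do not support that: the dipstick and the other triggers still lead to it. Nor can a number of missed AESIs be stated, since the documents give no rate of proteinuria below 2+. Raw urine protein results would still appear in the summaries and listings (Sections 13.7 and 13.7.2). What can be lost is the mandated collection and, with it, the AESI classification and the stopping-rule check.

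This takes the protocol's thresholds as written and makes no claim that they are wrong. It merits a correction in the next amendment because the risk is a named one.

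**What to change.** Add urine creatinine and urine albumin to footnote n, measured on the sample already collected, so that both ratios are reported at each quantitative urine visit. If the Laboratory Manual already covers them, name them in footnote n and cite the manual.

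The cost is one footnote line and at most 780 assays over the whole study, with no extra visit or blood draw. Urine creatinine is not a new assay for the trial: the stopping criterion "Measured GFR (creatinine clearance") of 45 mL/min/1.73 m² or less already requires it on a 24-hour collection. The downside is some extra confirmatory tests and 24-hour collections in young children under the existing thresholds. Their number cannot be calculated from the documents.

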4. LIST OF ABBREVIATIONS AND DEFINITIONS OF TERMS

Abbreviation	Definition
AE	adverse event
AESI	adverse event of special interest
ALT	Alanine aminotransferase
AST	Aspartate aminotransferase
AUC	Area under the time-concentration curve
BMD	Becker muscular dystrophy
CK	creatine kinase
CRO	contract research organization
CT	Computed tomography
DMC	Data Monitoring Committee
DMD	Duchenne muscular dystrophy
DNA	deoxyribonucleic acid
ECG	electrocardiogram
eCRF	electronic case report form
eGFR	Estimated glomerular filtration rate
GDPR	General Data Protection Regulations
GFR	Glomerular filtration rate
GGT	gamma-glutamyl transferase
GLDH	Glutamate dehydrogenase
HIPAA	Health Insurance Portability and Accountability Act
IEC	Independent Ethics Committee
INR	International normalized ratio
IP	investigational product
IRB	Institutional Review Board
IV	intravenous(ly)
MedDRA	Medical Dictionary for Regulatory Activities
MRI	magnetic resonance imaging
mRNA	messenger ribonucleic acid
CCI	CCI score
OLE	open-label extension
PMO	phosphorodiamidate morpholino oligomer

Abbreviation	Definition
PODCI	Pediatric Outcomes Data Collection Instrument
PT	preferred term
RBC	Red blood cell
RNA	ribonucleic acid
SAE	serious adverse event
SAP	Statistical Analysis Plan
SOC	system organ class
SUSAR	suspected unexpected serious adverse reaction
TEAE	treatment-emergent adverse event
ULN	upper limit of normal
WHODrug	World Health Organization Drug Dictionary

5. INTRODUCTION

5.1. Background of Duchenne Muscular Dystrophy

Duchenne muscular dystrophy (DMD) is a rare (estimated incidence of 1 in 5,000 live male births; [CDC 2009](#), [Emery 1991](#)), degenerative, X-linked, recessive genetic disorder caused by mutations in the dystrophin gene. In DMD, mutations in the dystrophin gene disrupt the open reading frame, resulting in an absence of functional dystrophin, a critically important part of the protein complex that connects the cytoskeletal actin of a muscle fiber to the extracellular matrix. In the absence of dystrophin, the stress of repeated muscle contraction causes cellular degeneration, regeneration, and inflammation, and, over time, myonecrosis.

The progression of DMD follows a highly predictable course. Significant motor deficits may be present during the first year of life, but diagnosis is usually made between the ages of 3 to 5 years when toddlers begin to show functional symptoms (eg, waddling gait, toe walking, and difficulty climbing stairs). Over time, ambulation becomes increasingly abnormal, and by 8 years of age, most patients lose the ability to rise from the floor and climb stairs, and often fall while walking. By 10 to 14 years of age, most lose the ability to walk. Upper limb, cardiac, and diaphragmatic muscles progressively weaken during adolescence. Historically, patients died from respiratory or cardiac failure in their late teens or early 20s ([Brooke 1989](#), [Eagle 2002](#)). Recent research suggests that use of ventilation support and steroids may increase life span by several years; however, DMD still has a mortality rate of 100% ([Kohler 2009](#)).

Existing interventions for DMD patients with mutations amenable to exon skipping are largely supportive in nature and include bracing, muscle-stretching exercises to avoid onset of contractures, tendon-release surgery, and eventual wheelchair use and assisted ventilation. Current pharmacologic treatments, such as corticosteroids, focus on alleviation of symptoms, but do not address the underlying cause of the disease. Corticosteroids may prolong ambulation, delay the onset of scoliosis, and improve performance on some measures of clinical function ([Beenakker 2005](#), [Biggar 2006](#), [Pradhan 2006](#)). However, their benefits are only temporary, and their use is often limited by numerous side effects, including growth inhibition, effects on pubertal changes, weight gain, behavioral changes, osteoporosis, Cushingoid facies and habitus, and cataracts ([Biggar 2006](#), [Manzur 2004](#)).

5.2. Phosphorodiamidate Morpholino Oligomers for the Treatment of Duchenne Muscular Dystrophy

Ribonucleic acid (RNA) therapeutics are compounds composed of heterocyclic nucleobases (adenine, cytosine, guanine, and thymine, or analogues) linked together on an oligomer backbone that supports hybridization via Watson-Crick base pairing with specific complementary RNA targets. RNA therapeutics can be synthesized to bind targeted RNA sequences in a pathogen or pathogenic process to treat a wide range of diseases through positively or negatively modulating gene expression.

A relatively new use of RNA therapeutics is to target a pre-messenger RNA (mRNA) in the nucleus of a cell to influence the splicing process that creates a mature mRNA. Referred to as “exon skipping,” this approach allows determination of which exons will be incorporated into the mature mRNA to be translated into the protein product.

Phosphorodiamidate morpholino oligomers (PMOs) are a class of synthetic molecules based on a redesign of the natural nucleic acid structure. Phosphorodiamidate morpholino oligomers are distinguished from natural nucleic acids and other oligonucleotide therapeutic platforms by the attachment of nucleobases to a 6-membered morpholine ring, as opposed to the 5-membered ribose ring found in RNA and deoxyribonucleic acid (DNA). Moreover, the morpholine rings are linked through neutrally charged phosphorodiamidate moieties, as opposed to negatively charged phosphodiester linkages in RNA and DNA. These differences were designed to increase stability and address safety issues seen with some earlier oligonucleotide backbone chemistries.

Phosphorodiamidate morpholino oligomers are capable of avid, sequence-specific binding *in vivo* to regulatory sites in pre-mRNA, and thus alter the splicing of a pre-mRNA transcript, such as that of dystrophin, causing the skipping (omission) of specific exons in the final mRNA. Approximately 80% of boys with DMD have out-of-frame deletions that could be amenable to exon-skipping therapies ([Aartsma-Rus 2009](#)). Several PMOs are being evaluated by Sarepta Therapeutics, Inc. (hereafter, “the Sponsor”) for the potential treatment of DMD, as exon skipping may enable the production of an internally deleted, functional dystrophin protein.

The active pharmaceutical ingredient of the investigational product (IP) eteplirsen injection is a charge-neutral PMO that selectively binds to exon 51 of the dystrophin pre-mRNA. In doing so, it causes the exon to be skipped during processing and restores the mRNA open reading frame in patients with mutations amenable to skipping exon 51 of the dystrophin gene, which is approximately 13% of all DMD patients ([Aartsma-Rus 2009](#)). This is expected to enable the production of an internally deleted, yet partially functional, dystrophin protein, similar to that observed in Becker muscular dystrophy (BMD), a much less severe form of dystrophinopathy. In contrast to DMD, most BMD patients remain ambulatory and have a near-normal life expectancy ([Bushby 1993](#)).

5.3. Clinical Experience with Eteplirsen

As of 24 June 2019, the eteplirsen clinical development program consists of 7 completed studies (Studies 4658-33, 4658-28, 4658-us-201, 4658-us-202, 4658-203, 4658-301 and 4658-204) and 2 ongoing studies (Studies 4658-102/102 OLE) in patients with DMD who were amenable to Exon 51 skipping. In addition, 2 Phase 1 studies (Studies 4658-101 and 4658-103) have been completed and 1 Phase 1 study (Study 4658-104) is ongoing in volunteers who do not have DMD.

Seven completed studies (Studies 4658-28, 4658-us-201, 4658-us-202, 4658-203, 4658-101, 4658-301 and 4658-103) have contributed to the pharmacokinetic profile of eteplirsen. There was little or no accumulation in plasma following weekly administration. Maximum plasma concentration and area under the concentration-time curve (AUC) increased in an approximately dose-proportional or slightly less than proportional manner. Urinary elimination of the active ingredient without metabolites was the predominant route of excretion. Based on the results of

Study **CCR**, an increase in eteplirsen exposure was observed in non-DMD adults with mild to moderate renal impairment.

Clinical efficacy results that include ambulatory and pulmonary function have been evaluated in completed Studies 4658-us-201/202, 4658-203, 4658-204 as well as Study 4658-301. Study 4658-us-201/202 provides long-term results across multiple ambulatory and respiratory endpoints over the course of 4 years. Studies 4658-301 (interim analysis) and 4658-204 provide additional supportive evidence of ambulatory and pulmonary function over the course of 2 years. Pooled results from these 3 studies (Studies 4658-us-201/202, 4658-203, and 4658-204) were compared with data from comparable external control cohorts and a comprehensive review of literature describing the natural history of DMD. Results from these analyses demonstrated a divergence, starting at Year 2, favoring eteplirsen-treated patients. Study 4658-301 confirmed mechanism of action showing increasing exon skipping leading to 0.52 % dystrophin levels by Western Blot which significantly & consistently increased over Baseline starting at Week 24 and continuing to Week 96 (n=77). Overall, the long-term safety profile of eteplirsen for treatment of patients with DMD was consistent with previous study data.

Study 4658-203 was a Phase 2, multicenter, open-label trial to evaluate the safety and tolerability of eteplirsen in patients aged 4 to 6 years with genotypically-confirmed DMD with genetic mutations amenable to treatment by exon 51 skipping. The study enrolled 26 patients who received once-weekly intravenous (IV) infusions of **CCR** mg/kg eteplirsen for up to 96 weeks. Treatment with eteplirsen was well tolerated and safety results were consistent with a favorable safety profile for eteplirsen. Analyses of clinical efficacy endpoints were exploratory in nature: in eteplirsen-treated patients, improvements from Baseline in functional motor abilities and health-related quality of life, Pediatric Outcomes Data Collection Instrument (PODCI) global functioning score, and 10-meter walk/run time were observed.

As of 24 June 2019, 182 patients with DMD and 59 non-DMD subjects have been treated with eteplirsen in clinical studies, including 175 who received IV eteplirsen and 155 who received **CCR** mg/kg or higher. Of the 182 patients, 17 and 135 patients received at least 48 and 96 weeks of eteplirsen treatment, respectively. This includes 12 patients from Study 201/202 who have been treated for over 5 years. These studies demonstrated that treatment with eteplirsen was generally well-tolerated at doses of **CCR** mg/kg (N=149) and 50 mg/kg (N=6) and there were no observed difference in safety between these 2 doses.

Based on the cumulative available safety data from these studies, eteplirsen has been shown to be well-tolerated, with low rates of serious or severe adverse events (AEs).

Refer to the eteplirsen Investigator's Brochure for further details.

